5. INCLUSION/EXCLUSION CRITERIA

Inclusion criteria:

- 1) Age 18-55
- 2) Female
- 3) Obese (BMI \geq 30kg/m²)
- 4) Not breastfeeding
- 5) Diagnosis of asthma, defined as

- Physician diagnosis of asthma, and
- Current treatment for asthma by a healthcare provider within the preceding twelve months. (Current asthma treatment defined as regular use of asthma medications. Asthma medications include short and long acting adrenergic bronchodilators, bronchodilator combinations, inhaled anticholinergics, inhaled corticosteroids, cromolyn sodium and nedocromil, leukotriene modifiers and methylxanthines.)

- 6) Stable asthma, defined by no asthma exacerbation (ED visit, course of increased systemic steroids, or urgent health care visit for asthma) during the prior four weeks.
- 7) Symptomatic asthma (Asthma Control Test <20 at baseline screening visit)
- 8) Non-smoker, defined by no cigarettes in the past year and a negative urine cotinine
- 9) No other major pulmonary disease such as cystic fibrosis or COPD
- 10) Willing to eat study diet and nothing else for each of the 6 days of controlled feeding

Exclusion criteria:

- 1) Chronic oral steroid therapy (daily)
- 2) Oral corticosteroid use within the past 4 weeks
- 3) Respiratory tract infection within the past 4 weeks
- 4) Significant medical issues such as heart disease or poorly controlled hypertension, type 1 diabetes, poorly controlled type 2 diabetes, or hypothyroidism that would interfere with collection of outcome measures or present safety issues in the opinion of the Principal Investigator
- 5) Pregnancy (self-report), planning a pregnancy, or nursing/breastfeeding mothers
- 6) Food allergy that interferes with ability to complete the study
- 7) Food preferences, intolerances, or dietary requirements that would interfere with diet adherence
- 8) Taking vitamin supplements
- 9) Planned dietary changes during the study period
- 10) Use of coumadin
- 11) Consumption of more than 14 alcoholic drinks per week, or consumption of 6 or more drinks on an occasion, one or more occasions per week
- 12) FEV₁<1.5L or <60% predicted post bronchodilator administration
- 13) Inability to perform acceptable spirometry
- 14) Any condition or compliance issue which in the opinion of the investigator might interfere with participation in the study
- 15) Lack of appropriate food refrigeration and preparation equipment (oven or microwave)
- 16) Inability to produce adequate sputum following induction with hypertonic saline neb

6. DRUGS/SUBSTANCES/DEVICES

a. The rationale for choosing the drug and dose or for choosing the device to be used.

Albuterol is a commercially available, FDA approved drug. We will administer albuterol according to ATS guidelines and as described elsewhere on this form.

b. Justification and safety information if FDA approved drugs will be administered for non-FDA approved indications or if doses or routes of administration or participant populations are changed.

Not applicable.

c. Justification and safety information if non-FDA approved drugs without an IND will be administered.

Not applicable.

7. STUDY STATISTICS

a. Primary outcome variable

Primary Outcome: Feasibility of intervention and study procedures. We will measure this via qualitative interviews at the feedback sessions.

b. Secondary outcome variables

Secondary Outcomes: We will also assess compliance with the dietary intervention via change in dietary markers; examples include serum lipids, serum fatty acids, and serum carotenoids. We will assess success of the study procedures based on success at obtaining serial induced sputum at follow-up visits. Based on previous findings that have demonstrated increases in inflammation (both Th1 and Th2) and oxidative stress among individuals with asthma or in response to diet exposure, we have selected a panel of biomarkers to be measured in study participants utilizing the resources and staff of the CCAUE. We will measure markers of Th1 inflammation (including sputum neutrophil %, neutrophil elastase, IL-8, and IL-6; serum TNF-alpha and IFN-gamma), markers of Th2 inflammation (including sputum eosinophil %, IL-5, and IL-13; FeNO; serum eosinophil %), and markers of oxidative stress (including sputum 8-isoprostane, serum RANTES, and urine 8-isoprostane). We will also evaluate stool samples, nasal swab samples, and sputum samples for microbiome and changes with each dietary intervention. We will also look at change in reported symptoms, self-efficacy in managing disease, and lung function between the Western and prudent diets. Lastly, we will also evaluate temporal variability in exposures (such as cleaning agents) that could be linked to respiratory effects and/or to other related health outcomes, including oxidative stress.

c. Statistical plan including sample size justification and interim data analysis

Analysis Plan: Participant feedback will be analyzed via a deductive approach for content analysis. We will examine for themes within the interview data which either support the current approach or suggest that procedure modification could improve feasibility and participant experience in a future trial. The distributions of all quantitative variables will be examined for outliers and missing data points. Next, the distributions of serum lipids, carotenoids, fatty acids, FEV₁, FeNO, and sputum neutrophil % will be summarized and displayed for each time point. Post-challenge levels of these outcome variables will be compared between prudent and Western diet interventions using paired t-tests, displaying the calculated differences as percentages and absolute differences. Group 1 will be defined as the group randomized first to the Western diet, and Group 2 will be defined as the group randomized first to the prudent diet. We will also evaluate for evidence of carryover effect (measurable effect from order of intervention), although the washout period has been carefully selected to prevent this. We will examine differences in the outcome variables by order of intervention occurrence and apply the t-test. If the outcomes do not appear normally distributed, we

will transform them so that they meet assumptions of normality. In addition, we will calculate the intraclass correlation coefficient (ICC) using mixed effects models to assess the temporal variability of target biomarkers. The ICC is a measure of reproducibility and commonly used to assess the suitability of biomarkers to properly characterize exposures.

Power Calculations: Power calculations cannot be completed for the primary, qualitative outcome of feasibility.

Sample Size: We propose a small study as a feasibility trial to generate preliminary data for a future, larger intervention that will be powered to detect clinical endpoints.

Study Duration: The duration of intervention, 6 days, is shorter than most other diet intervention studies to date. Our prior intervention was of one-month duration, with outcomes similar at two weeks and one month. Other trials of diet intervention in asthma have also been at least two weeks in duration, though this duration of meal replacement is costly and difficult to scale. Importantly, just four hours after a high-fat diet challenge, meaningful changes in lung function and inflammatory markers have been detected, suggesting the presence of short-term effects on asthma health. We intend to further evaluate these short-term effects, both a novel and important aspect of the proposal that will inform duration and timing of outcome assessment in the planned, future trial. Based on variability of the secondary outcomes assessed in this trial and degree and directionality of change seen, we anticipate that this pilot will inform both feasibility as well as necessary duration of a future, definitive trial.

As this is a pilot study, we do not intend to complete interim analyses.

d. Early stopping rules

As this is a pilot study, there will be no formal criteria for stopping the study early, however participants may choose to leave the study early or may leave the study early at the determination of the Principal Investigator.

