1. ABSTRACT

Background: In the U.S., increased intake of fast food and highly processed foods (a “Western-style” diet) has been coincident with the dramatic rise in asthma. Observational studies demonstrate a link between a dietary pattern and asthma morbidity at the level of the individual, and limited trials of counselling for a healthier diet have shown promise in improving asthma health.

Objectives: The objective of the study is to demonstrate the feasibility of a randomized, controlled trial of complete dietary replacement (feeding study) in a population of adults with asthma, and to provide measures of variability in the proposed outcomes (symptoms, lung function, markers of inflammation and oxidative stress) to inform sample size calculation for a larger, definitive trial.

Methods: The study is a feasibility trial of a prudent (high in fruit and vegetables, whole grains, low-fat dairy) versus Western-style (high in processed foods, fast food, sweets) diet intervention in adults with asthma. Eight to twelve adult women (ages 18-55) who meet eligibility criteria will be enrolled. At baseline, demographic information, asthma symptom scores, usual dietary intake, anthropometric measures and DEXA, spirometry, FENO, blood, urine, nasal, and sputum samples will be collected. Participants will then be randomized to either the Western-style diet or a prudent diet. Prior to initiating the diet, they will have assessment of select biologic outcomes (FENO, spirometry, symptom assessment, biomarkers of oxidative stress and inflammation in urine and serum, and nasal swab). After 6 days of the randomized diet, they will repeat these assessments and undergo induced sputum for local (pulmonary) biomarkers of inflammation and oxidative stress. The participants will then have a 4-8 week washout period, and repeat the same order of assessments prior to and after receiving the alternate diet assignment. During each of the 6-day interventions, participants will record asthma-related symptoms via a standardized questionnaire. At the final session, participants will provide feedback on the acceptability and palatability of the dietary interventions and assessments. As this is a feasibility study, we will use results to assess the process and procedures necessary to scale the intervention to a larger study population.

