4. STUDY PROCEDURES

a. Study design summary

Figure 1. Study Design

Experimental Design, BREATHE-Easy Trial

We will conduct a single-blinded (study staff only), randomized crossover pilot trial to evaluate the feasibility of a Western and prudent diet feeding study in Baltimore City adults with asthma (Figure 1). The results from this study will provide data to inform a larger trial evaluating the differential effects of a Western-style (high in processed foods, fast food, sweets) diet and a prudent (high in

fruit and vegetables, whole grains, low-fat dairy) diet on symptoms, lung function, systemic inflammation, and local airway inflammation among adult asthmatics.

Potential study subjects will undergo phone screening prior to invitation for initial clinic visit. Participants will be consented at initial clinic visit, after which they will complete additional eligibility testing (urine pregnancy testing, urinary cotinine measurement, induced sputum collection, and if eligible undergo baseline assessments (demographic information, baseline questionnaire, usual dietary intake evaluation, anthropometric measures, DEXA, spirometry, FeNO, blood, urine, and nasal sample collection). Participants will then be randomized to initiate a Western-style diet or prudent diet and scheduled a date to return for their first assessment (A1) prior to initiating the assigned intervention. FeNO, spirometry, symptoms/questionnaires, and nasal swab, urine, stool/fecal strip, and serum collection will occur at first assessment. Participants will then receive 3 days of meals to take home. Participants will return at day 3 to retrieve the last 3 days of meals (or alternatively, the last 3 days of meals will be delivered to their place of residence), and will return again at day 6 to repeat the assessments at A1 + sputum induction. During each of the Western and prudent intervention diet periods, participants will complete daily questionnaires/diaries on food consumed, symptoms, and other potential exposures that may affect asthma control. Participants will then have an approximately 4-8 week washout period during which they will be instructed to resume their regular diet before continuing with the alternate dietary intervention with mirrored assessments. At the second A2 visit, participants will be asked to answer questions regarding acceptability and tolerability of study schedule and participant flow, and to report comments on study acceptability ad libitum.

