Energy values and macronutrient distribution (as percent of kilocalories) will be similar for the prudent and Western diet with a goal of 35-37% Fat, 45-47% Carbohydrate, and 16-18% Protein. Differences between the diets are defined in the table below.

Nutrient or Food Pattern	Western Diet	Prudent Diet
Saturated fat (% of kcals)	≥10	<8
Omega-6:Omega-3 ratio	≥13:1	≤5:1
Whole grains (% of grain servings)	0	100
Fruit (servings/day)	≤1	≥3
Vegetable, not potato (servings/day)	≤1	≥3
Nuts (1 oz. serving/day)	0	≥1
Fish (3 ounce serving 4/6 days)	0	2
Processed meat (ounces/day)	≥3	0
Sweets (30-125 gram serving/day)	≥1	0
Sugar sweetened beverages (fluid ounces/day)	≥8	0

Food Production and Distribution:

Meals will be prepared and distributed in the research kitchen of the Nutrition Core at the ICTR. The research kitchen is inspected annually by the Baltimore City Health Department. Managers and staff of the ICTR research kitchen are certified through ServeSafe. Participants will be instructed in food safety.

Promotion of Adherence: Efforts to promote adherence begin at the earliest stages of the study. During the phone and in-person screenings, participants are repeatedly provided with information about key features of the study. During the phone screening, participants will complete the Diet Screening Form, which includes a detailed list of foods provided. Individuals must be willing to eat

each of these foods; otherwise, they are excluded. Key contacts with nutrition staff include an in-person evaluation by a dietitian. The intent of these efforts is to identify and exclude, prior to randomization, participants who are unwilling or unable to comply with the feeding protocol.

Efforts to promote adherence center on making the foods palatable and convenient to the participant lifestyles; maintaining easy access to staff; and providing available, daily, supportive contacts. Acceptance of the controlled feeding protocol is increased by allowing participants to consume pre-approved selected beverages, as well as an unlimited amount of water and artificially sweetened soft drinks.

Assessment of Adherence

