- 4) Urine collection:** Prior to enrollment, all participants will submit a urine sample for pregnancy testing, and urine will also be collected for analysis at each assessment visit. Urine biomarkers, including LTE₄ and F-isoprostane, will be measured to assess oxidative stress and inflammation.

We will also measure other markers of inflammation/chemical exposure that may affect asthma control. Any excess urine will be stored for future analyses.

- 5) **Stool/Fecal strip sample:** One sample will be collected to analyze gut microbiome at baseline and during each follow-up visit. Sample will be stored at -80°C until further analysis of gut microbiome.
- 6) **Symptom report** via questionnaires including the Asthma Quality of Life Questionnaire (AQLQ), Asthma Symptom Utility Index (ASUI), and the Asthma Control Test (ACT). The AQLQ has been validated for individuals 15 and older and is designed to measure daily impact of asthma in patients' lives. The ASUI is a validated 2-week recall questionnaire that addresses issues of asthma control weighted by impact on functional status. Participants will also complete daily symptom diaries during the 6 days of intervention. The ACT is a validated 4-week recall of symptoms and functioning.
- 7) **Nasal swab collection:** Nasal swab (and optionally, oropharyngeal and skin swab) collection will occur at each assessment visit, before and after each dietary intervention, to obtain a sample for cellular examination. Analysis of biomarkers in nasal specimens will include (1) cell count and differential, (2) cytokines, (3) chemokines, and other markers of inflammation, (4) microbial assessment.

Daily Diaries:

During the course of each feeding period, participants will complete daily diaries (questions and format supplied) to document data such as adherence to the diet, use of cleaning products, symptoms and albuterol use. Participants will be contacted daily with reminders to complete the diaries and to allow for any participant questions or concerns. Telephone calls or text messages will be used for this purpose.

Assessment 2 (after the dietary intervention period) will include all of the above assessments, plus:

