- 8) **Sputum induction:** Participants will be instructed through an induced sputum procedure via hypertonic saline nebulization. Sputum inductions and processing will be performed following published protocols. Briefly, after baseline spirometry, an ultrasonic nebulizer will be used to deliver hypertonic saline for at most a total of 20 minutes. The subject will be asked to expectorate sputum into a specimen cup placed on ice. Lung function will be monitored to ensure participant safety. If there is a fall in FEV₁ of $\geq 20\%$ compared baseline FEV₁ prior to sputum induction at any point or if the patient is unwilling or unable to continue, sputum induction will be terminated and albuterol administered as needed.
- 9) **Feedback session:** We will solicit feedback on acceptability of intervention and satisfaction with study structure, including study instruments administered to optimize participant experience and retention for an anticipated, larger-scale trial.

b. Study duration and number of study visits required of research participants

Each study participant will be enrolled for a maximum of approximately 16 weeks, and with rolling enrollment we anticipate completion of all study visits within 1 year. Each research participant will be required to attend a baseline clinic visit and four assessment clinic visits. In addition, during each of the Western and prudent intervention periods, the participants will be required to pick up their meals at most twice: once at initial assessment, and mid-way through the intervention period, they

may either return to the clinic to pick up the remainder of their meals or their meals will be delivered to their home. In total, each research participant will be required to make five to seven study-related visits.

c. Blinding, including justification for blinding or not blinding the trial, if applicable.

It is not possible to blind participants to this protocol, as they will be aware which diet they have been assigned. Participants will be randomized using a computerized random assignment table with permuted blocks to receive either the “Western” or “prudent” diet first, and they will receive the alternate diet after the washout period. We will blind investigators and all study staff outside of the nutrition CRU staff to diet assignment.

d. Justification of why participants will not receive routine care or will have current therapy stopped.

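### The primary feasibility outcome rests on interviews placed at the last visit, so women who leave early are not heard, although the feedback is meant to improve retention

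*Combined protocol and SAP*

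**What the plan says.** Section 7.a names feasibility as the primary outcome and gives one way of measuring it: "We will measure this via qualitative interviews at the feedback sessions". The Analysis Plan in section 7.c is confined to the same source: "We will examine for themes within the interview data which either support the current approach or suggest that procedure modification could improve feasibility".

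The timing of the feedback is described in several places:

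- Abstract: "At the final session, participants will provide feedback on the acceptability and palatability of the dietary interventions and assessments".
- Section 4.a, design summary: "At the second A2 visit, participants will be asked to answer questions regarding acceptability and tolerability of study schedule and participant flow".
- Section 4.a.iv lists the feedback session as item 9 under this lead-in: "Assessment 2 (after the dietary intervention period) will include all of the above assessments, plus". Nothing there limits it to the second period. Its stated purpose is "to optimize participant experience and retention for an anticipated, larger-scale trial".
- Section 10 pays a bonus for finishing the whole study, with a single feedback session counted as part of finishing.

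Sections 4.f and 7.d allow a woman to leave early, by her own choice or by the Principal Investigator's decision. Section 4.g covers premature exit but mentions only diet. No exit interview is described anywhere.

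There are other contacts during feeding. Under Daily Diaries: "Participants will be contacted daily with reminders to complete the diaries and to allow for any participant questions or concerns". Under Promotion of Adherence, staff aim at "providing available, daily, supportive contacts". No contact is described during the washout of about 4-8 weeks. Section 7.b lists dietary markers and success at serial sputum induction as secondary outcomes. Section 7 defines no measure of screening yield or of completion among randomised women.

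**The concern.** The trial exists to judge whether a larger feeding trial can be run, and a woman's reason for leaving is direct evidence on that. Under the plan, whether she is interviewed depends on whether she completes, and completion is itself part of feasibility. If leavers differ from completers, the themes will make the trial look more workable than it was. Nothing in the analysis would show this, because no completion figure is set beside the themes.

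The gap matters most for retention, which is a stated purpose of the feedback. It is also hard to repair later. Completion counts can be rebuilt from records, but reasons for leaving are difficult to obtain months afterwards.

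**Working it through.** The plan gives no power, dropout rate or target for the primary outcome, so there is no stated figure to reproduce. The check has four parts.

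**1. Who is heard on each reading of the timing**

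| Woman leaves | Feedback at final visit only (abstract, 4.a, 10) | Feedback at both A2 visits (possible reading of 4.a.iv) |
|---|---|---|
| In period 1, before the first A2 | Not interviewed | Not interviewed |
| In washout or period 2 | Not interviewed | Interviewed once, before leaving; not asked why she left |
| Completes | Interviewed | Interviewed |

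Leavers' reasons are missing on both readings.

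**2. Time without described contact**

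Inputs from section 4.a: two 6-day feeding periods and a washout of 4-8 weeks (28-56 days).

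- First A1 to second A2: 6 + 28 + 6 = 40 days, up to 6 + 56 + 6 = 68 days.
- Washout share: 28/40 = 70% to 56/68 = 82%.

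This is calendar time. It shows how long the daily contacts are absent, not how many women leave then.

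**3. Chance that a barrier to participation is missed (final-visit reading)**

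Inputs: n = 8 or 12 (section 4.a.i). Dropout d = 5%, 10%, 20% is assumed. Expected leavers are n × d: 0.4, 0.8, 1.6 for n = 8, and 0.6, 1.2, 2.4 for n = 12. The chance of at least one leaver, 1 − (1 − d)^n, is 34%, 57%, 83% for n = 8 and 46%, 72%, 93% for n = 12.

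Suppose k women hold a barrier, they leave independently, and every holder who completes reports it. It is missed only if all k leave.

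- Unrelated to leaving: probability d^k.
- Related, with odds ratio OR: let p0 be the leaving probability for other women and p1 = OR·p0 / (1 − p0 + OR·p0) for holders. Solve [k·p1 + (n − k)·p0]/n = d, so that overall dropout stays at d. Probability missed = p1^k.

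Worked case: n = 8, k = 1, d = 10%, OR = 5. The solution is p0 = 0.0736 and p1 = 0.2845. Check: (0.2845 + 7 × 0.0736)/8 = 0.100. Missed: 28.5%.

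| Holders | Link to leaving | d = 5% | d = 10% | d = 20% |
|---|---|---|---|---|
| 1 | None | 5% | 10% | 20% |
| 1 | OR 2 | 9% | 17% | 31-32% |
| 1 | OR 5 | 15-17% | 28-31% | 49-51% |
| 2 | None | 0.25% | 1% | 4% |
| 2 | OR 2 | 0.6-0.7% | 2-3% | 8-9% |
| 2 | OR 5 | 1.4-2.0% | 5-7% | 18-21% |

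Ranges run from n = 8 to n = 12. The odds ratios are assumptions too.

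**4. What a completion rate could show**

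Exact (Clopper-Pearson) 95% intervals: 8/8, 63-100%; 7/8, 47-99.7%; 6/8, 35-97%; 12/12, 74-100%; 11/12, 62-99.8%; 10/12, 52-98%. These are too wide to support a pass/fail threshold, but they state plainly how little is known.

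**The case against.** The strongest reply is that the documents are silent on exit interviews rather than ruling them out, and that the assessment list, with the plural used for the sessions in section 7.a, could mean feedback at both A2 visits. On that reading a woman who leaves in washout or period 2 has already been heard once. This stands as a qualification. It does not help a woman who leaves in period 1, and no leaver is asked why she left. Section 10 also points to a single session tied to completion.

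Second, there are other routes: daily contacts and diaries, the daily compliance score, adverse-event and deviation reports, the missing-data check, and sputum success, which partly tracks attendance. The abstract also says results in general will be used to judge process. These narrow the gap. But none is set up to record why a woman left, none is assigned to the primary feasibility analysis, and the daily contacts are not described for the washout.

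Third, the size rests on assumed dropout rates and odds ratios, and the washout share says nothing about when women leave. That is right. With twofold odds, or with two holders, the figures are much smaller. Short feeding periods, careful screening and payments may keep losses near zero.

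Fourth, no stated analysis becomes invalid, and completion counts can be tabulated later. Also true. Only the exit contact and the timing wording are urgent.

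**Conclusion.** The concern holds and should be fixed. As written, the primary content analysis rests on completers if feedback is at the final visit. If it is at both A2 visits, the analysis omits period 1 leavers and every leaver's reasons. Section 7 has no completion or screening measure that would reveal the omission.

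The effect ranges from none, if nobody leaves, to about an even chance of missing a barrier held by one woman, at an assumed 20% dropout and fivefold odds. It is small if leavers share completers' views, if several women hold the same barrier, or if leavers' concerns were already recorded in daily contacts that are then analysed. Confidence is medium: the text is clear enough, but how many women would leave is unknown.

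**What to change.** 1. **Timing and exit interview (before enrolment).** Reconcile the abstract, section 4.a and section 4.a.iv on when feedback is taken. Seek a brief telephone exit interview from each randomised woman who leaves early, where possible by someone who neither supplies the meals nor measures outcomes. State in section 7.c that these interviews, and concerns already recorded in daily contacts, enter the content analysis. Keep any diet feedback given before the end of period 2 from staff who are blinded under section 4.c.

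2. **Counts beside the themes.** Report the numbers screened in person, passing sputum induction, randomised, and completing each period. Give completion among all randomised women with an exact 95% confidence interval, descriptively and without a threshold. A phone-screen count is optional and needs a simple prospective log. Reporting the 0-3 compliance score is also optional.

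**Cost.** Protocol wording, about 0-3 short calls in total at 0-20% dropout, and counts that study records should already hold. The new contact may need IRB approval and consent wording. Some leavers will decline. In a small team the interviewer may have to be nutrition staff, and answers may then be more favourable. The feasibility figures may also look less good.
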